9.4.3 ANALYSIS OF THE PRIMARY SAFETY ENDPOINT

The primary safety endpoint in this study is the rate of vaginal cuff dehiscence through six months. Vaginal cuff dehiscence is defined as rupture of the surgical wound requiring surgical re-intervention. Subjects who experience vaginal cuff dehiscence up to six months after surgery will also be considered a cuff closure failure.

The number and proportion of subjects with vaginal cuff dehiscence at 6 weeks will be presented. The 95% confidence interval of the proportion will also be reported.

9.4.4 ANALYSIS OF SECONDARY EFFICACY ENDPOINTS

Secondary Endpoint (1) Cuff closure (compared between test and reference groups) will be assessed (yes or no) by an independent surgeon at one and six weeks, as well as at six months.

Data collection: Surgeon will visually assess vaginal cuff closure, indicating whether the vaginal mucosa is intact. If the vaginal cuff closure is determined not to be intact, then failure of this study endpoint will be indicated and the subject will be included in the ITT population for remaining study endpoints. If additional surgical intervention is necessary to address lack of cuff closure, follow-up will restart following the new procedure date. In this circumstance the new follow-up schedule will be included in the evaluation of remaining efficacy endpoints in the ITT population and will be included in the safety population.

Acceptance Criteria: Endpoint success at each timepoint is defined as test group cuff closure failure rate less than or equal to that of the reference group.

Statistical Analysis Method: A two-sided Fisher's Exact Test will compare (test versus reference) rate of dehiscence at each timepoint. Assessment of this endpoint is independent of primary study endpoint results.

Secondary Endpoint (2) Cuff healing (compared between test and reference groups), will be assessed (yes or no) by an independent surgeon at six weeks and six months.

Data collection: Surgeon visual assessment of cuff healing is limited to a single binary assessment ("healed" or "not healed"). Additional descriptive observations are included during data collection but are not used in comparative analysis. If the vaginal cuff is determined not to be healed, then failure of this study endpoint will be indicated. If additional surgical intervention is necessary, follow-up will restart following the new procedure date. In this circumstance the new follow-up schedule will be included in the evaluation of remaining efficacy endpoints in the ITT population and will be included in the safety population.

Acceptance Criteria: Endpoint success is defined as a test group cuff healing failure rate less than or equal to that of the reference group.

Statistical Analysis Method: A two-sided Fisher's Exact Test will compare (test versus reference) rate of visually assessed, failed cuff healing at each post-operative timepoint. Assessment of this endpoint is independent of the primary safety endpoint.

Secondary Endpoint (3) Comparison of implant passing rates.

Data collection: Implant passing rates will be calculated and the percentage of subjects experiencing one or more implant passing events will be compared between the test and control groups at six weeks and at six months.

Acceptance Criteria: Endpoint success is defined as a percentage of subjects experiencing implant passing in the test group less than or equal to that of the reference group.

Statistical Analysis Method: A two-sided Fisher's Exact Test will compare (test versus reference) percentage of subjects experiencing implant passing events between test and reference groups. Assessment of this is independent of the primary study endpoints.

Secondary Endpoint (4) Relationship of Implant passing to Adverse Events.

Data collection: Frequency of implant passing events associated with an Adverse Event will be evaluated through six-weeks post-operative. Associating implant passing to an Adverse Event will include consideration of temporal and possible causal relationship. The AE relatedness terms described in Section 8.3.3 will be utilized in determination of implant passing to a given Adverse Event, where "relatedness to study intervention" is replaced with "relatedness to implant passage." This will not replace determination of relatedness to the study device, which will be performed separately according to study safety reporting details. Adverse Events determined to be 'probably' or 'definitely' related to an implant passing event will be considered a per patient failure of the primary efficacy endpoint. Relationship of implant passing events to AEs will be reported independently and compared between test and control groups.

Acceptance Criteria: Endpoint success is defined as a percentage of subjects experiencing implant passing event related to an AE in the test group less than or equal to that of the reference group.

Statistical Analysis Method: A two-sided Fisher's Exact Test will compare (test versus reference) percentage of subjects experiencing implant passing event associated with an AE between test and reference groups. Assessment of this is independent of the primary study endpoints.

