9.2 SAMPLE SIZE DETERMINATION

The study size was based on FDA's recommendation of the sufficient sample size to support a future 510(k) notification.

A minimum of 30 and a maximum of 40 subjects in the test group have been requested for this study. Assuming a 10% loss to follow-up, a goal of 39 (maximum of 44) subjects are expected to be enrolled in the test group, and a goal of 20 (maximum of 22) are expected to be enrolled in the reference group, for a total goal of 59 (maximum of 66).

No statistical assessment of the rate of successful cuff closure is required for analysis of the primary study endpoints. The rate of implant passing events on a per-patient basis will be numerically compared to the 5% performance target. Nonetheless, the 95% confidence interval will be reported for this endpoint.

This study is also not powered to address secondary endpoints. It is not expected that statistical analyses will yield conclusive results on exploratory endpoints.

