9.4.5 ANALYSIS OF SECONDARY SAFETY ENDPOINTS

The Safety population will be the analysis population for all safety analyses.

Secondary Endpoint (5) Comparison of incidence of adverse events.

Data collection: Adverse Events will be tabulated for both the test and reference groups. All AEs and SAEs will be MedDRA-coded and summarized by treatment arm. In addition, the number and proportion of AEs and SAEs will be calculated for each group. For each MedDRA-coded medical term, the proportion of subjects who experience at least one of the following will be reported and compared.

Adverse event

- Adverse event related to treatment
- Serious adverse event
- Serious adverse event related to treatment
- Adverse event leading to study discontinuation
- Serious adverse event leading to study discontinuation

Classification of AEs will also be presented and compared. Events will be reported by MedDRA system organ class and preferred term. Adverse Events will be compared by severity and device relatedness between the test and reference groups.

Acceptance Criteria: There is no defined endpoint acceptance criteria for the comparison of adverse events.

Statistical Analysis Method: A two-sided Fisher's Exact Test will compare (test versus reference) rate of incidence of adverse events by six months post-operative. Assessment of this is independent of the primary study endpoints.

Secondary Endpoint (6) Comparison (test to reference group) of non-increase in subject dyspareunia scores from baseline to 6-months post-operative.

Data collection: Individual subject dyspareunia will be assessed using the relevant sexual discomfort module of the validated Female Sexual Function Index (FSFI). Higher scores indicate good sexual function with little or no sexual discomfort, and lower scores indicate poor sexual function with higher levels of sexual discomfort. Scores of zero indicate no sexual activity and will not be included in comparison of non-increase in dyspareunia.

Acceptance Criteria: A subject level failure is defined as a decrease in sexual function score (signifying an increase in dyspareunia). Endpoint success is defined as the same or lower rate of FSFI score decrease in the test group at six months when compared to the reference group at six months.

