Statistical Analysis Method: Comparison (test versus reference group) of failure rates from baseline to six-month follow-up will be made using a two-sided Fisher's Exact Test. Assessment of this is independent of the primary study endpoints.

Secondary Endpoint (7) Comparison (test to reference group) of non-increase in subject pain scores from baseline to 6-months post-operative.

Data collection: Individual subject pain will assed using a validated 11-point numerical pain rating scale, where "0" corresponds to no pain and "10" corresponds to the most pain possible. Pain score will be collected at all study timepoints and unexpected visits; however, statistical assessment will be performed between baseline and six-month score.

Acceptance Criteria: A subject level failure is defined as an increase in reported subject pain score. Endpoint success is defined as the same or lower rate of increase in reported pain in the test group at six months when compared to the reference group at six months.

Statistical Analysis Method: Comparison (test versus reference group) of failure rates from baseline to six-month follow-up will be made using a two-sided Fisher's Exact Test. Assessment of this is independent of the primary study endpoints.

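### Six of seven secondary endpoints declare success on a bare comparison of observed failure rates, with no margin or confidence bound, although the plan calls them exploratory and unpowered

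*Combined protocol and SAP*

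**What the plan says.** Sections 9.4.4 and 9.4.5 attach an acceptance criterion to six of the seven secondary endpoints.

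- Endpoint 1, cuff closure: "Endpoint success at each timepoint is defined as test group cuff closure failure rate less than or equal to that of the reference group".
- Endpoint 2, cuff healing: "Endpoint success is defined as a test group cuff healing failure rate less than or equal to that of the reference group".
- Endpoint 3, implant passing: success requires the percentage "experiencing implant passing in the test group less than or equal to that of the reference group". Endpoint 4, passing related to an adverse event, is worded the same way.
- Endpoint 6, dyspareunia: "Endpoint success is defined as the same or lower rate of FSFI score decrease in the test group at six months", compared with the reference group.
- Endpoint 7, pain: "Endpoint success is defined as the same or lower rate of increase in reported pain in the test group at six months", compared with the reference group.

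Endpoint 5 is the exception: "There is no defined endpoint acceptance criteria for the comparison of adverse events".

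Each endpoint also has a two-sided Fisher's exact test, but the criterion does not refer to it.

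On status, the synopsis heads these endpoints as exploratory. Section 4.2 says they are meant to show possible trends, and section 9.2 states: "This study is also not powered to address secondary endpoints". The synopsis and the objectives table in section 3 nevertheless give the secondary objective as demonstrating safety and efficacy against the suture reference.

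**The concern.** A rule that compares two observed proportions returns a verdict whatever the uncertainty. With about 20 women in the reference arm and uncommon events, that verdict can rest on one patient. It can also disagree with the test printed beside it: 1/39 against 0/20 misses the criterion, while Fisher's test gives p = 1.0.

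The plan states no operating characteristics for the rule. At stake is the meaning of six success or failure labels in the study reports. Section 3 says data through six months may support market clearance, so an equivalent device could be labelled a failure, or a worse one a success, largely by chance.

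**Working it through.** **Inputs from the plan**

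- Enrolment target (synopsis; sections 4.1 and 9.2): 39 test and 20 reference, from 35 evaluable test subjects and 10% loss. This reproduces: 35/0.9 = 38.9, so 39; 39/2 = 19.5, so 20; total 59. Section 9.2 allows up to 44 and 22.
- Reference failure rates: none is given for closure, healing, pain or dyspareunia. The nearest figures are dehiscence of up to 5% (section 2.3.1) and implant passing expected below 10% (section 4.2). Dehiscence is narrower than a cuff graded not closed, so 5% is an assumption here and a range is needed.

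**Formula**

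Let X ~ Bin(n_T, p_T) and Y ~ Bin(n_R, p_R) be independent failure counts. Then P(success) is the sum over y of P(Y = y) × P(X ≤ floor(y·n_T/n_R)).

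**Worked case: 39 vs 20, reference rate 5%**

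| Reference failures y | P(Y = y) | Test failures allowed | P(X within limit), p_T = 5% | P(X within limit), p_T = 10% |
|---|---|---|---|---|
| 0 | 0.3585 | 0 | 0.1353 | 0.0164 |
| 1 | 0.3774 | 1 | 0.4129 | 0.0876 |
| 2 | 0.1887 | 3 | 0.8709 | 0.4437 |
| 3 | 0.0596 | 5 | 0.9877 | 0.8097 |
| 4 or more | 0.0159 | 7 or more | about 1.00 | about 0.97 |

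- Equivalent device: 0.0485 + 0.1558 + 0.1643 + 0.0588 + 0.0159 = 0.443. It fails 55.7% of the time.
- Twice the failure rate: 0.0059 + 0.0331 + 0.0837 + 0.0482 + 0.0154 = 0.186.
- Better device (2% vs 5%), same method: 0.734.
- The reference arm has no failures with probability 0.95^20 = 0.358. In that case a single test failure fails the endpoint.

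**Over assumed reference rates, 39 vs 20**

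| Reference rate | Equivalent device fails | Device with twice the rate succeeds |
|---|---|---|
| 1% | 27.5% | 52.4% |
| 2% | 41.4% | 33.8% |
| 3% | 49.1% | 25.3% |
| 5% | 55.7% | 18.6% |
| 7.5% | 57.1% | 14.9% |
| 10% | 56.4% | 12.1% |
| 20% | 53.7% | 4.6% |
| 30% | 52.1% | 1.2% |

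**Over arm sizes, reference rate 5%**

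| Test vs reference | Equivalent device succeeds | Device with twice the rate succeeds |
|---|---|---|
| 30 vs 15 | 56.5% | 31.7% |
| 35 vs 18 | 45.4% | 19.7% |
| 36 vs 18 | 55.9% | 29.2% |
| 39 vs 20 | 44.3% | 18.6% |
| 40 vs 20 | 55.6% | 27.7% |
| 44 vs 22 | 55.4% | 26.4% |

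The jump between 39 and 40 test patients comes mainly from one configuration. Against one reference failure in 20 (5.00%), two test failures in 39 (5.13%) miss the criterion, while two in 40 (5.00%) meet it. Fisher's p is 1.0 in both cases.

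**The case against.** The plan is open about the limits. It labels the endpoints exploratory, disclaims power, expects no conclusive exploratory results and concedes in section 4.2 that the small reference group weakens comparison. It says these assessments are independent of the primary endpoints. No gate, labelling claim or stopping decision is tied to a success label. A direction of difference and a significance test answer different questions, so their disagreement is not itself a contradiction. All of this stands, and it limits the consequence. It does not explain why endpoints meant to show trends carry a pass/fail rule.

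A reader might infer that every secondary endpoint fails an equivalent device half the time and passes a doubled-risk device one time in five. The documents do not support that. The second figure needs a reference rate near 5% and arms of exactly 39 and 20, and the first breaks down for rare events (27.5% at 1%). Endpoint 6 will have fewer women than the target, because scores of zero are excluded.

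A reader might also infer that the verdicts are coin flips in general. That fits only a truly equivalent device. At an assumed 5% reference rate the rule passes a better device (2%) 73% of the time and a doubled-risk device 19% of the time.

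**Conclusion.** The point holds as a defect of the rule and not as one fixed error rate. Six criteria issue success or failure from observed rates alone, without error control in either direction, on endpoints the plan itself calls exploratory and unpowered.

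At 39 vs 20 and an assumed 5% reference rate, an equivalent device fails about 56% of the time and one with twice the failure rate succeeds about 19%. Across reference rates of 1% to 30% the latter runs from 52% to 1%. An equivalent device fails 27.5% of the time at 1% and roughly half the time (49% to 57%) at 3% and above. At 5%, a single extra test patient moves these success chances from 44% to 56% and from 19% to 28%.

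The figures assume independent binomial counts, complete data and one verdict at one timepoint. The primary endpoints and the sample size are unaffected.

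**What to change.** In sections 9.4.4 and 9.4.5, delete the acceptance criteria for endpoints 1 to 4, 6 and 7, which brings them into line with endpoint 5. For each, report the difference in proportions (test minus reference) with an exact 95% confidence interval beside the Fisher p-value, and carry the synopsis's exploratory label into these sections. The synopsis already promises 95% intervals, so the new elements are the effect measure and the interval method. The interval matters because Fisher's test alone says little here: at 39 vs 20 its power for 10% vs 5% is about 1.6%.

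The cost is a minor protocol revision, since the criteria stand in the protocol's own sections and section 9.4.10 refers to a separate SAP. The sponsor gives up a success label on unpowered endpoints. Visits, data collection and sample size do not change.

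Keeping a formal verdict would be a different study. As an illustration only, assume a 10-point non-inferiority margin, 5% failure in both arms, one-sided 0.025, 80% power and 2:1 allocation. The reference arm then needs (1.960 + 0.842)² × 0.05 × 0.95 × 1.5 / 0.10² = 56 women, with 112 in the test arm.

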3.2 SECONDARY ENDPOINTS

(1) Binary assessment of cuff closure

Cuff closure will be assessed by an independent surgeon at one and six weeks, as well as at six months. Surgeon visual assessment will grade vaginal cuffs as closed or not closed, or the surgeon may indicate that it was not possible to determine. As such, subjects who experience a dehiscence and are considered a failure in analysis of the primary study safety endpoint will be a failure in this secondary endpoint (lack of closed cuff at six weeks). However, subjects could fail this secondary endpoint without failing the primary study safety endpoint.

In cases in which a surgeon is unable to assess cuff closure, the most recent successful evaluation of cuff closure (including intra-operative evaluation) will be used; reason for inability to determine will be recorded. Fisher's Exact Test will be used to assess possible significance of a difference in cuff closure scores between test and reference groups.

(2) Binary assessment of cuff healing

Vaginal cuff healing will be visually assessed by an independent surgeon at six weeks and six months. Surgeon visual assessment will grade vaginal cuffs as healed or not healed, or the surgeon may indicate that it was not possible to determine. In cases in which a surgeon is unable to assess cuff healing, the most recent successful evaluation of cuff closure will be used. If no prior evaluation has established cuff healing, the cuff will be assumed to have not healed yet. Reason for inability to determine healing will be recorded. Fisher's Exact Test will be used to assess possible significance of a difference in cuff closure scores between test and reference groups. Additionally, healing will be characterized using a predetermined list of binary assessment questions, these will not be statistically compared, but serve to characterize individual healing scores.

(3) Comparison of implant passing rates

The percentage of subjects experiencing implant (either clip or suture) passing by six-weeks and six-months post-operative will be compared between test and control groups using Fisher's Exact Test.

(4) Frequency of implant passing events associated with an Adverse Event

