10.2 ABBREVIATIONS AND DEFINITIONS

Adverse Events (AE)

For the purpose of this clinical investigation plan, an adverse event (AE) is any untoward medical occurrence, unintended disease or injury or any untoward clinical signs in subjects whether or not related to the Investigational Product and includes events related to the procedures involved (any procedure in the clinical investigation plan). All Adverse Events (including serious Adverse Events) will be classified by outcome, severity, treatment taken, and attribution to study intervention. See Section 8.3 for more details.

Associated Adverse Event

Defined as an AE that is both device-related (to either clip or reference device in accordance with Section 8.3.3) and that is temporally related to the implant passing event.

Body Mass Index (BMI)

Code of Federal Regulations (CFR)

Vaginal Cuff Dehiscence

Vaginal cuff dehiscence has a reported incidence of up to one in twenty (5%) among patients undergoing laparoscopy^{5–7} even with robotic assistance.⁸ Vaginal cuff dehiscence has been defined in this study as a rupture of the surgical wound requiring surgical re-intervention. Small openings in approximated vaginal mucosa that resolve without intervention will be recorded as part of cuff closure and healing characterization endpoints, but will not be deemed as failures, since intervention was not required to bring about recovery

Food & Drug Administration (FDA)
Good Clinical Practice (GCP)
Informed Consent Form (ICF)
Institutional Review Board (IRB)
Instructions For Use (IFU)
Investigational Device Exemption (IDE)

Laparoscopic Assisted Vaginal Hysterectomy (LAVH)

LAVH is the surgical excision of a women's uterus using a combination of vaginal and laparoscopic approaches LAVH typically includes laparoscopically detaching the uterine body from the surrounding upper supporting structures. The vaginal apex is entered using a vaginal approach, and the cervix and uterus are detached from the remaining supporting structures. The uterus is then removed through the vagina.

Poly-p-dioxanone (PDO)

A biologically inert, bio-absorbable polymer that degrades naturally by hydrolysis. Both traditional suture and Zip-stitch[™] clips are composed of this material.

Principal Investigator (PI)

Serious Adverse Events (SAE)

Serious AEs are a subset of AEs. An SAE is one that:

- Results in death
- Results in life-threatening illness or injury
- Results in a permanent impairment of a body structure or function

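### Section 9.4.4 tests the cuff-closure endpoint on the dehiscence rate, contradicting its own failure rule and acceptance criterion, Section 3.2 and the synopsis

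*Combined protocol and SAP*

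**What the plan says.** Section 9.4.4 describes secondary endpoint (1) in three short paragraphs:

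- Data collection: "If the vaginal cuff closure is determined not to be intact, then failure of this study endpoint will be indicated".
- Acceptance criterion: "Endpoint success at each timepoint is defined as test group cuff closure failure rate less than or equal to that of the reference group".
- Statistical method: a two-sided Fisher's test, test against reference, of the "rate of dehiscence at each timepoint".

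Section 9.4.3 gives the meaning of the last term: "Vaginal cuff dehiscence is defined as rupture of the surgical wound requiring surgical re-intervention". Section 3.2 has the surgeon grade each cuff as closed, not closed or not determinable. It counts every dehiscence as a closure failure and adds that "subjects could fail this secondary endpoint without failing the primary study safety endpoint". Both Section 3.2 and the synopsis (Section 1.1) apply Fisher's exact test for this endpoint to cuff closure scores.

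The entry for vaginal cuff dehiscence in Section 10.2 says that small mucosal openings which resolve unaided are recorded under the closure and healing endpoints, "but will not be deemed as failures, since intervention was not required to bring about recovery". It does not name the endpoint to which that last clause applies.

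**The concern.** The failure rule and acceptance criterion concern one event and the test concerns another. By the plan's own account closure failure contains dehiscence and is wider. The difference between them is the set of cuffs seen to be open that never needed re-operation. Those cases are what this endpoint adds to the primary safety endpoint, and the test as written in 9.4.4 would leave them out.

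There are two consequences. First, the report could state success or failure on the closure failure rate beside a p-value that describes dehiscence. Second, at six weeks the test would largely overlap the between-group dehiscence comparison already set in Section 3.1.

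The Section 10.2 wording makes this worse. A reader could use it to exempt a cuff graded not closed at one week because the opening later healed. Such choices should be settled before the database lock and unblinding that Section 6.3 places after the last six-week visit. The table in Section 3 treats closure as a basic measure of efficacy, and data through six months may support market clearance.

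**Working it through.** **1. The texts side by side**

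| Place | Variable for endpoint (1) |
|---|---|
| Synopsis, secondary efficacy (1) | Fisher's test on cuff closure scores |
| Section 3.2 (1) | Fisher's test on cuff closure scores |
| Section 9.4.4 (1), data collection | Failure = cuff not intact |
| Section 9.4.4 (1), acceptance criterion | Closure failure rate, test no higher than reference |
| Section 9.4.4 (1), statistical method | Fisher's test on dehiscence |

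Four of the five use closure and one uses dehiscence. The parallel text for endpoint (2) in 9.4.4 tests failed healing, the same event as its failure rule. This suggests that the wording for endpoint (1) is a slip.

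**2. Relation of the two events**

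Section 3.2 makes every dehiscence a closure failure and allows closure failures without dehiscence. So:

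closure failures = dehiscences + open cuffs needing no re-operation.

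The two tests agree only if the second term is zero in both arms, or happens not to matter.

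**3. Group sizes (Sections 1.1 and 9.2)**

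- Test arm: 35 / (1 − 0.10) = 38.9, rounded up to 39.
- Reference arm: 39 / 2 = 19.5, rounded up to 20.
- Total: 39 + 20 = 59, as the plan states.

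**4. How much a dehiscence test can show**

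The documents quote a dehiscence incidence of up to 5%. At that upper figure:

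- Expected dehiscences: 0.05 × 39 = 1.95 (test) and 0.05 × 20 = 1.0 (reference).
- Probability of none in the test arm: 0.95^39 = 0.135.

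Counts this small say little about closure.

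**5. Effect of the chosen variable (assumed counts)**

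The documents give no rate for openings that need no surgery. As an assumption, take 1 dehiscence in the test arm and 0 in the reference arm, with all further open cuffs in the test arm. Two-sided Fisher p-values for 39 versus 20:

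| Variable tested | Test | Reference | p |
|---|---|---|---|
| Dehiscence | 1/39 | 0/20 | 1.00 |
| Closure failure, 2 further open cuffs | 3/39 | 0/20 | 0.54 |
| Closure failure, 4 further | 5/39 | 0/20 | 0.16 |
| Closure failure, 6 further | 7/39 | 0/20 | 0.083 |
| Closure failure, 7 further | 8/39 | 0/20 | 0.042 |
| Closure failure, 8 further | 9/39 | 0/20 | 0.022 |

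With no reference failures, 8 test-arm failures is the smallest count giving p ≤ 0.05. After 10% loss (35 versus 18) it is also 8 (p = 0.040). In the other direction, 0/39 versus 3/20 gives p = 0.035. The tested variable can therefore change the result, but in the device's disfavour only with a large excess of open cuffs.

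**The case against.** The strongest reply is that the closure comparison is in the plan. The synopsis and Section 3.2 both specify it, and the acceptance criterion in 9.4.4 compares closure failure rates. That stands. A reader might infer from 9.4.4 alone that closure is never compared between arms, and the documents do not support this: they specify the comparison and contradict it in one sentence. Nor would non-surgical openings vanish from the data. They would still be graded at each visit, marked as endpoint failures, counted in the acceptance criterion and listed by participant (Section 9.4.9). They would be missing only from the test.

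A reader might also say that the 9.4.4 test simply repeats the primary safety comparison. That goes too far. The Section 3.1 comparison runs through six weeks on the Safety population, as treated. Endpoint (1) is analysed on the ITT population, as randomized, at one week, six weeks and six months. Both populations contain all randomized subjects and differ only where the treatment received was not the one assigned, so the six-week overlap would be large but is not identity.

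Finally, a reader might infer from Section 10.2 that small openings are both failures and not failures. The sentence sits inside the definition of dehiscence, and its stated reason, that no intervention was needed, follows that definition. Its most natural meaning is *not dehiscence failures*, which agrees with Section 3.2. This is an ambiguity, not a proven contradiction.

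The reply does not remove the mismatch itself. Section 9.4.4 is the detailed analysis section, and its test names a variable that its own failure rule does not use.

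**Conclusion.** The point holds as an internal contradiction about the tested variable. Followed literally, Section 9.4.4(1) tests dehiscence where the rest of the plan for this endpoint uses closure failure. It would leave out cuffs graded not closed that needed no re-operation, and at six weeks it would largely overlap the comparison in Section 3.1. The Section 10.2 wording is a lesser matter that needs clarifying.

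The impact is limited. The endpoint is secondary, the synopsis labels it exploratory, and Section 9.2 says the study is not powered for it. Neither primary endpoint changes, and no figure in the plan is wrong. The size cannot be derived from the documents. The illustration rests on assumed counts, on the planned 39 versus 20, and on no reference failures. Under those assumptions the result moves to p ≤ 0.05 only at 8 or more test-arm closure failures. The correction is worth making because it costs almost nothing and removes a choice that could otherwise be made after the data are seen.

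**What to change.** In Section 9.4.4(1), replace the tested rate in the statistical method with *rate of cuff closure failure (cuff graded not closed)*, so that it matches the synopsis, Section 3.2 and the section's own acceptance criterion.

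In Section 10.2, state that the sentence about small openings not being failures refers to the dehiscence endpoint, and that an opening graded not closed at a visit still counts under secondary endpoint (1).

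Make both changes before database lock. The cost is wording in two sections, with no new data, visits or subjects. The tested failure rate may be somewhat higher than a dehiscence rate would be, because it counts the wider event.
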